1.1. Brief Background

Physical activity is well-documented to provide benefits beyond physical health, including improvements in cognitive functions such as memory, attention, processing speed, and executive functions. Aerobic exercise, in particular, has been shown to enhance cognitive performance by promoting neurogenesis, synaptic plasticity, cerebral blood flow, and reduced inflammation. Among all forms of aerobic activity, **walking** stands out due to its simplicity, low cost, and accessibility across various populations.

While the benefits of exercise on cognition are established, there is limited consensus on the **optimal duration and frequency** required to achieve these effects. Health authorities like the World Health Organization (WHO) endorse accumulating physical activity in bouts of at least 10 minutes throughout the day, but direct comparisons of **short-duration, high-frequency** versus **long-duration, continuous** walking on cognitive outcomes in young, healthy adults are sparse.

1.2. Rationale for the Study

Despite the evidence supporting exercise for cognitive enhancement, many individuals—especially students and working adults—struggle to engage in long-duration workouts due to time constraints or physical limitations. Shorter, more frequent bouts of walking may offer a **feasible alternative** for achieving cognitive benefits. However, there is limited clinical evidence directly comparing these two approaches in a **controlled, randomized trial** setting.

This study addresses a critical knowledge gap by evaluating whether **three short walking sessions (10 minutes each)** throughout the day are as effective as a **single continuous 30-minute session** in improving cognitive function in sedentary young women. The results will help inform more accessible, time-efficient exercise prescriptions aimed at preserving and improving cognitive health.

1.3. Objectives and Hypotheses

Primary Objective:

To compare the effects of two different walking protocols (short-duration vs. long-duration) on cognitive function, specifically **processing speed and executive function**, in sedentary young adult females over a 6-week intervention.

Secondary Objective:

To evaluate changes in attention, inhibition control, and overall cognitive flexibility through various subtests of the Stroop Test following each walking protocol.

Primary Hypothesis (H₁):

Both short-duration and long-duration walking exercise protocols will lead to significant improvements in cognitive performance after 6 weeks.

Secondary Hypothesis (H₂):

There will be **no significant difference** in cognitive improvement between the two groups, indicating that **short, frequent bouts** of walking are **as effective** as a longer, continuous session.

2. Study Design

This study was conducted as a **randomized controlled trial** using a **parallel assignment model** to compare the effects of two different walking protocols on cognitive function in sedentary young adult females. Participants were randomly assigned in a 1:1 ratio to either a **short-duration walking group** or a **long-duration walking group**. The intervention period lasted for **six weeks**, with both groups engaging in walking exercise **five days per week**.

The **short-duration group (experimental arm)** performed **three separate 10-minute walking sessions** daily, while the **long-duration group (active comparator arm)** completed **one continuous 30-minute walking session** per day. In both groups, walking was performed on a treadmill at **60% of each participant's maximum heart rate**, calculated using the formula (220 - age). Heart rate was monitored during sessions using treadmill sensors and cross-checked with a pulse oximeter to ensure consistency. Standardized warm-up and cool-down periods were applied to both protocols.

Randomization was conducted using the Research Randomizer tool (Version 4.0), and allocation concealment was maintained throughout the study. Although participants were aware of their assigned protocol (due to the nature of the intervention), the study employed **double masking**: the **investigator supervising the exercise sessions** and the **outcomes assessor conducting cognitive tests** were both blinded to group assignments to minimize bias.

This design aimed to investigate whether short, frequent bouts of aerobic exercise provide comparable cognitive benefits to longer, continuous sessions, potentially offering a more flexible and accessible option for individuals with time constraints.

3.

This study was conducted at the Faculty of Health Sciences, Gazi University, in the Department of Physiotherapy and Rehabilitation. Ethical approval was obtained from the Ethics Committee of Gazi University with the record number 2023- 1134 to conduct the study.

4. Participants

Participants in this study were **female individuals aged 18 to 25 years** who maintained a **sedentary lifestyle**, defined as taking fewer than 5000 steps per day. Additional inclusion criteria included being a **non-smoker**, having the **physical ability to walk on a treadmill**, maintaining a **work or school schedule compatible with the intervention schedule**, and providing **written informed consent**.

Exclusion criteria included having a **body mass index (BMI) of 30 kg/m² or higher**, a history of **neurological or severe cardiovascular conditions**, participation in another **regular exercise program** during the study period, any **physical limitation that would interfere with safe walking**, and **pregnancy**. These criteria were established to ensure the safety of participants and to maintain the homogeneity of the study population.

5. Interventions

Participants were randomly assigned to one of two intervention groups. The **experimental group** performed **three 10-minute walking sessions per day**, while the **active comparator group** completed **one continuous 30-minute walking session per day**. Both groups exercised **five days per week for six weeks**. The intensity of the exercise was standardized at **60% of the participant's maximum heart rate**, calculated using the formula $(220 - \text{age})$. Heart rate was continuously monitored using treadmill-integrated sensors and confirmed with pulse oximeter readings. Standardized warm-up and cool-down periods were integrated into both protocols.

6. Outcomes

The **primary outcome** of the study was the **change in Digit Symbol Substitution Test (DSST) scores** from baseline to post-intervention (6 weeks), reflecting improvements in **processing speed and executive function**.

Secondary outcomes included changes in performance on three subtests of the **Stroop Test**, which evaluated various aspects of cognitive function.

7. Sample Size and Power

A power analysis was conducted using **G*Power 3.1** software. Based on an expected **effect size of 0.5**, a **power of 95%**, and a **significance level of 0.05**, the **minimum required sample size** was determined to be **34 participants**, with **17 in each group**. This calculation ensured that the study would be adequately powered to detect meaningful differences between groups.

8. Randomization

Randomization was performed using the online tool **Randomizer.org (Version 4.0)** to generate a computer-based random sequence, ensuring unbiased allocation of participants. A **1:1 allocation ratio** was used. Although participants were aware of their assigned walking schedules, **both the investigator supervising the training sessions and the assessor performing the cognitive tests were blinded to group assignment** to maintain objectivity in outcome evaluation.

9. Data Collection and Management

Cognitive function assessments were conducted at **baseline** and again **after the 6-week intervention**. All data were anonymized and stored securely in password-protected digital files accessible only to the research team. To ensure adherence, participants maintained **daily exercise logs**, and researchers conducted routine follow-ups throughout the intervention period. Any protocol deviations or dropouts were documented.

10. Statistical Analysis Plan (SAP)

Statistical analysis was performed using **SPSS version 24**. The **normality of distribution** for outcome variables was tested using the **Shapiro-Wilk test**. **Independent samples t-tests** were used to compare baseline values between groups, while **ANCOVA** was applied to adjust for any baseline differences when comparing post-intervention outcomes. **Paired t-tests** were used to evaluate within-group changes from baseline to post-intervention.

Effect sizes were calculated using **Cohen's d** to quantify the magnitude of observed changes. A **p-value of less than 0.05** was considered statistically significant. **Outliers** were identified through **z-score analysis** and **visual inspection of boxplots**. In cases of dropout or incomplete data, **listwise deletion** was applied, and only participants who completed both pre- and post-tests were included in the final analysis.

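### The primary hypothesis claims that walking improves cognition within each arm; a trial with no non-walking arm cannot test this, and it does not match the comparative primary objective

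*Protocol*

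**What the plan says.** Protocol section 1.3 states the primary objective as a comparison of the two arms: "To compare the effects of two different walking protocols (short-duration vs. long-duration) on cognitive function". The primary hypothesis (H1) in the same section is different: "Both short-duration and long-duration walking exercise protocols will lead to significant improvements in cognitive performance after 6 weeks". The between-group question comes only in the secondary hypothesis (H2): "There will be no significant difference in cognitive improvement between the two groups".

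Section 2 describes two arms, three 10-minute walks a day or one 30-minute walk a day, "with both groups engaging in walking exercise five days per week". No non-walking arm is described. Sections 2 and 8 say that participants knew their assigned schedule.

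Section 7 sets 17 participants per group and says that this makes the study "adequately powered to detect meaningful differences between groups". Section 9 fixes two test occasions: "Cognitive function assessments were conducted at baseline and again after the 6-week intervention". Section 10 lists a between-group test, "ANCOVA was applied to adjust for any baseline differences when comparing post-intervention outcomes", and a within-group test: "Paired t-tests were used to evaluate within-group changes from baseline to post-intervention". It does not say which test serves which hypothesis.

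**The concern.** The objective and the hypothesis that are both labelled primary ask different questions. The objective asks whether one protocol does better than the other. H1 asks whether scores rise in each arm, and its wording makes walking the cause.

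Randomisation protects the first question only. Anything that raises scores equally in both arms, such as having taken the test before, expecting to improve, or the passage of six weeks, cancels in the between-group comparison but counts fully towards H1. The hypothesis with the primary label could therefore be declared confirmed, and a cognitive benefit of walking reported, when walking did nothing.

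**Working it through.** **1. Which question each element addresses**

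| Element | Protocol section | Question |
|---|---|---|
| Primary objective | 1.3 | Between arms |
| Primary hypothesis H1 | 1.3 | Within each arm, causal |
| Secondary hypothesis H2 | 1.3 | Between arms |
| Purpose of the sample size | 7 | Between arms |
| ANCOVA | 10 | Between arms |
| Paired t-tests | 10 | Within each arm |

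Among the listed tests, only the paired t-test can address H1. It can validly show that scores changed. With no non-walking arm, it cannot show that walking changed them.

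**2. The Protocol's own figure.** It gives no figure for H1. The sample size in section 7 (34 in total, from effect size 0.5, power 95%, alpha 0.05) is for between-group differences. It does not reproduce: a two-sided two-sample t-test needs 105 per group, and a two-sided paired t-test at the same settings needs 54. That is a separate matter. Here 17 per arm is taken as given.

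**3. How often H1 would be confirmed with no walking effect**

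Inputs from the Protocol: n = 17 per arm and alpha 0.05. Assumptions:
- the test is two-sided (the Protocol does not say);
- there is one outcome per arm, the DSST, as the single primary outcome;
- a retest gain g, in SDs of the change score, is equal in both arms. The Protocol gives no value, so a range is shown.

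Formula: the paired t statistic has df = 17 − 1 = 16 and noncentrality g√17. Per arm, p = P(T > 2.120), where 2.120 is the 97.5% point of t with 16 df. The arms are independent, so both improve with probability p². For example, at g = 0.5 the noncentrality is 0.5 × 4.123 = 2.06, p = 0.491, and p² = 0.241.

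| g (SD of change) | One arm | Both arms |
|---|---|---|
| 0 | 0.025 | 0.0006 |
| 0.1 | 0.058 | 0.0034 |
| 0.2 | 0.118 | 0.0140 |
| 0.3 | 0.213 | 0.0453 |
| 0.4 | 0.341 | 0.116 |
| 0.5 | 0.491 | 0.241 |
| 0.8 | 0.872 | 0.760 |
| 1.0 | 0.972 | 0.944 |

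The joint rate reaches 5% at g = 0.309 and 50% at g = 0.647.

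**4. The same situation under the between-group ANCOVA.** Simulation with 20,000 runs, 17 per arm, assumed pre-post correlation r = 0.7, equal retest gain and no group difference:

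| g | ANCOVA rejects | Both paired tests show improvement |
|---|---|---|
| 0 | 5.0% | 0.05% |
| 0.5 | 5.1% | 24.1% |
| 1.0 | 4.9% | 94.6% |

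An equal gain leaves the ANCOVA at its nominal level and drives the paired tests.

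**5. Precision of the ANCOVA.** The approximate 95% CI half-width, in SDs of the score, is t(31 df) × √(2/17) × √(1 − r²) = 2.04 × 0.343 × √(1 − r²). This is 0.61, 0.50 and 0.42 at assumed r = 0.5, 0.7 and 0.8. Intervals this wide mean that a non-significant result alone cannot show that the protocols are equally effective.

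**The case against.** **The randomised comparison is already planned, so this is only labelling.** It is true that no test is missing. The objective, the sample-size statement and the ANCOVA are between-group, and the Protocol labels a hypothesis, an objective and an outcome as primary, but not an analysis. The label still matters, because it marks the answer to H1 as the trial's main result, and H1 is the claim that randomisation does not protect.

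**Promoting the ANCOVA does not answer the study's real question.** The rationale in section 1.2 asks whether short bouts are as good as one long session. A test for a difference, with no margin and 17 per arm, cannot establish that. This stands. The change corrects the primary hypothesis but does not supply an equivalence or non-inferiority design.

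**The Protocol is written in the past tense.** Exchanging hypotheses after conduct carries its own risk. This also stands, and it is why the change must be disclosed if analysis has been done.

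**The figures depend on choices.** H1 speaks of cognitive performance, and section 6 lists the DSST plus three Stroop subtests. At a gain of 0.5 SD, with four outcomes and an assumed correlation of 0.3 between their change scores, the joint rate is about 2% if all four must improve in both arms, 59% if the same outcome must improve in both, and 74% if any outcome in each arm suffices. With one outcome and a one-sided test it is 40% (0.629²). One two-sided test per arm is a reasonable reading, since only the DSST is primary. The alternatives change the size of the rate, but under none of them can a within-arm change be attributed to walking.

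**Conclusion.** The concern holds and must be fixed. H1 is a causal within-arm claim that this design cannot test, and it conflicts with the primary objective in the same section.

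The size of the false-confirmation risk depends on a retest gain that the Protocol does not give. Under equal gains in both arms and one two-sided test per arm, small gains rarely confirm H1 falsely (1.4% at 0.2 SD of change), while moderate or large gains often do (24% at 0.5 and 76% at 0.8). The validity problem does not rest on these figures: even a real and correctly detected rise in scores could not be credited to walking.

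**What to change.** - Make the baseline-adjusted ANCOVA of 6-week DSST between groups the single primary analysis, reported with its 95% CI, and restate the primary hypothesis as that between-group difference.
- Report the mean change with 95% CI and Cohen's d for each arm as description only, and state that the change cannot be attributed to walking because there is no non-walking arm.
- State that a non-significant ANCOVA will not be read as showing equal effectiveness. That claim needs a margin set in advance and a matching sample size, which is a separate point.
- If the data have already been analysed, disclose the change of primary hypothesis as post hoc.

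**Cost:** no new data and no new test. The sponsor gives up the claim that both protocols cause improvement and, if analysis is complete, must make the post hoc disclosure.

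### H2 treats a non-significant difference as evidence that short bouts work as well as one long session, with no margin or confidence-interval rule

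*Protocol*

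**What the plan says.** H2 in section 1.3 states: "There will be no significant difference in cognitive improvement between the two groups, indicating that short, frequent bouts of walking are as effective". It is labelled secondary, but the same question is the declared purpose elsewhere. Section 1.2 says the study evaluates whether three 10-minute sessions "throughout the day are as effective as a single continuous 30-minute session", and expects the results to inform exercise prescriptions. The closing paragraph of section 2 says: "This design aimed to investigate whether short, frequent bouts of aerobic exercise provide comparable cognitive benefits to longer, continuous sessions".

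The analysis in section 10 is built on tests of difference. Between groups, "ANCOVA was applied to adjust for any baseline differences when comparing post-intervention outcomes"; within groups, paired t-tests are used. The only decision criterion is "A p-value of less than 0.05 was considered statistically significant". Cohen's d is calculated to describe magnitude, with no threshold attached. Section 7 describes a trial "adequately powered to detect meaningful differences between groups". The document contains no equivalence or non-inferiority margin and no rule based on a confidence interval.

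**The concern.** A p-value of 0.05 or more says that the data are compatible with no difference. It does not say that they are incompatible with a difference that matters. Read as H2 reads it, the rule also rewards imprecision: the smaller or noisier the trial, the easier it is to conclude that the short protocol is equally good. Completers-only analysis with listwise deletion pushes the same way, because each dropout widens the interval.

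At stake is the between-group conclusion, the one meant to guide prescriptions. A result that leaves a sizeable deficit of the short arm open could be reported as showing that short bouts do as well. H1, which concerns improvement within each group, is not affected.

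**Working it through.** **Inputs from the Protocol.** 17 per group and 34 in total, effect size 0.5, power 95%, significance level 0.05 (section 7); ANCOVA on post-intervention scores, p < 0.05 (section 10); primary outcome DSST change over 6 weeks (section 6).

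**Assumptions.** The Protocol does not say which metric the 0.5 is in, and gives no baseline/post correlation r. Below, d is the true deficit of the short arm in SDs of the post-intervention score, tests are two-sided at 0.05, and r is varied.

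**The Protocol's own figure.** With 0.5 read as Cohen's d, 95% power and a two-sided 0.05 level, a two-sample t-test needs 105 per arm, not 17. The 34 does not reproduce under this reading. That is a separate matter, and the argument here does not depend on it. What counts is that 17 per arm is the planned size.

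**Step 1: how often would a real deficit be read as equal effectiveness?** Unadjusted, P(non-significant) = P(|T| ≤ t(0.975, 32)), where T is noncentral t with 32 degrees of freedom and noncentrality d × √(17/2). For d = 0.5 the noncentrality is 0.5 × 2.915 = 1.458, which gives 0.707. The ANCOVA values come from simulation with 200,000 trials per cell.

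| True deficit (d) | Unadjusted | ANCOVA r = 0.5 | r = 0.7 | r = 0.8 |
|---|---|---|---|---|
| 0.3 SD | 86% | 84% | 78% | 72% |
| 0.5 SD | 71% | 64% | 51% | 36% |
| 0.8 SD | 38% | 27% | 13% | 4% |
| 1.0 SD (0.5 read as Cohen's f) | 19% | 11% | 3% | 0.4% |

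The last row applies because, with two equal groups, d = 2f = 2 × 0.5 = 1.0.

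**Step 2: what can the interval exclude?** The 95% half-width is t(0.975, 31) × √(2/17) × √(1 − r²) = 2.040 × 0.343 × √(1 − r²).

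- r = 0: 0.70 SD
- r = 0.5: 0.61 SD
- r = 0.7: 0.50 SD
- r = 0.8: 0.42 SD

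Even an observed difference of exactly zero would leave a 0.5 SD deficit inside the interval at r = 0 or 0.5, and would be borderline at r = 0.7.

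**Step 3: the perverse direction.** Unadjusted, at d = 0.5, non-significance rises from 71% with 17 per arm to 78% with 12. The 12 is only an illustration, since the Protocol gives no dropout figure.

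**Step 4: what would a proper test offer at this size?** Take an assumed non-inferiority margin of 0.5 SD, one-sided 0.025, no true difference and 17 per arm. Power is about 28%, 36%, 50% and 64% at r = 0, 0.5, 0.7 and 0.8. For 80% power about 65, 49, 34 or 25 per arm would be needed.

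**The case against.** The strongest reply is about weight. H2 is secondary and worded as a prediction, and section 10 never states that p ≥ 0.05 will be declared equal effectiveness. Reporting an adjusted difference with its interval is often left to a separate analysis plan, and section 10 already includes Cohen's d. The percentages run from 0.4% to 86%, depend on an unstated r and on which SD is meant, and largely reflect low power. The Protocol is in the past tense, so a new margin or sample size may be moot.

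Part of this stands. No single percentage is established. The range under the planned ANCOVA is more relevant than the unadjusted figure, and the choice of SD matters. If the 0.5 were in SDs of change, then at r = 0.8 it would equal 0.5 × √(2 × (1 − 0.8)) = 0.32 post-score SD, and non-significance would be about 70% instead of 36%. That shift strengthens the concern. The absence of an interval would not by itself be a finding against a protocol.

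The core is untouched. H2 itself writes the step from non-significance to equal effectiveness, and nothing elsewhere qualifies it. Cohen's d without an interval or a threshold cannot rule out a deficit. The secondary label carries little weight when the primary objective is to compare the two protocols and the rationale and design aim both ask about comparability.

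**Conclusion.** The concern holds. The inference in H2 is wrong as written, and no sample-size figure is needed to show it. The size depends on assumptions about the effect-size metric and r. For a true deficit of 0.5 SD of the post score and 17 per arm, the planned ANCOVA would be non-significant in about 36% to 64% of trials for r between 0.8 and 0.5. For 0.3 SD the range is 72% to 84%. Only for large deficits combined with high correlation does the risk become small. Because this reading supports the study's main practical conclusion, it must be corrected. The within-group hypothesis H1 stands apart from this point.

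**What to change.** - In H2, delete the step from no significant difference to equal effectiveness.
- In section 10, add one sentence: the ANCOVA-adjusted DSST difference (short minus long) is reported with its 95% confidence interval, together with a statement of which deficits of the short arm it does and does not exclude.
- Only if a justified margin in DSST points can still be fixed before the data are examined, state a non-inferiority or equivalence hypothesis. Claim non-inferiority only when the interval excludes a deficit of that size, and equivalence only when it lies wholly within both margins. Otherwise report that it was not shown.
- Whatever the result against the margin, if the interval lies wholly below zero, report that the short arm was significantly worse, and do not describe it as equally effective without that qualification.

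The cost is small: wording in H2 and one reporting sentence, with the interval coming from the model already planned. Because the Protocol is written in the past tense, a margin may no longer be possible, and one chosen after seeing the data should not be used. The real price is that, with 34 participants, the comparability result may well be inconclusive. If the trial is still open, the per-arm sizes in Step 4 show what an assumed 0.5 SD margin would require.

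### The exercise supervisor cannot be blinded to arms defined by visible session length and number, so the double-masking claim fails and at most the outcomes assessor is masked

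*Protocol*

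**What the plan says.** Protocol section 2 (Study Design) states that "the study employed double masking: the investigator supervising the exercise sessions and the outcomes assessor conducting cognitive tests were both blinded to group assignments". Section 8 (Randomization) says the same in other words: "both the investigator supervising the training sessions and the assessor performing the cognitive tests were blinded to group assignment", and gives the purpose as "to maintain objectivity in outcome evaluation". Section 2 concedes that "participants were aware of their assigned protocol", and attributes this to the nature of the intervention.

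The arms are described in sections 2 and 5. The experimental group "performed three separate 10-minute walking sessions daily"; the comparator group "completed one continuous 30-minute walking session per day". The rest of the schedule is shared: "Both groups exercised five days per week for six weeks", on a treadmill, at the same percentage of age-predicted maximum heart rate, with standardized warm-up and cool-down in both protocols. On monitoring, section 2 says: "Heart rate was monitored during sessions using treadmill sensors and cross-checked with a pulse oximeter to ensure consistency".

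**The concern.** Session length and session number are the treatment contrast itself. A person who supervises the walking watches exactly the feature that distinguishes the arms, so a claim that this person did not know the group conflicts with the description of the intervention. The protocol accepts this reasoning for participants, who could not be masked because of what the intervention is. The same visible feature is open to the supervisor.

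What is at stake is how far a reader can trust the between-arm comparison. The secondary hypothesis is that short bouts work as well as one long session. If supervisor and participant both know the arm, encouragement or support for adherence could differ between arms. A reader who takes the masking statement at face value would discount that possibility.

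**Working it through.** The protocol gives no figure to reproduce on this point. The check sets the two arm descriptions side by side and asks what a supervisor could fail to see.

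**Inputs** (Protocol sections 2, 5 and 7): 5 days per week; 6 weeks; 3 sessions of 10 minutes per day or 1 session of 30 minutes per day; 17 participants per group.

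**Counts per participant, every session attended**
- Training days, both arms: 5 × 6 = 30.
- Long-duration arm: 30 × 1 = 30 sessions; 30 × 30 min = 900 min.
- Short-duration arm: 30 × 3 = 90 sessions; 90 × 10 min = 900 min.

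**Counts per arm at the planned size**
- Long-duration arm: 17 × 30 = 510 sessions.
- Short-duration arm: 17 × 90 = 1,530 sessions.

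**Comparison of the arms**

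| Feature | Short-duration arm | Long-duration arm | Differs? |
|---|---|---|---|
| Mode | Treadmill | Treadmill | No |
| Intensity | 60% of (220 − age) | 60% of (220 − age) | No |
| Days and weeks | 5 per week, 6 weeks | 5 per week, 6 weeks | No |
| Total walking time | 900 min | 900 min | No |
| Warm-up and cool-down | Standardized | Standardized | Per session or per day not stated |
| Session length | 10 min | 30 min | Yes |
| Sessions per day | 3 | 1 | Yes |

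**Reasoning**
1. The clearly stated differences are session length and sessions per day. If warm-up and cool-down were given with every session, that would be one more visible difference.
2. A supervised walk either stops at 10 minutes or runs on to 30. One complete session therefore reveals the arm. The counts show how the arms differ; the argument does not need many sessions.
3. The protocol describes no arrangement that would keep this from the supervisor. Rotating staff would not help, because a single complete session is enough.
4. Allocation concealment, which section 2 mentions separately, protects the assignment before it is made. It cannot hide a treatment that is being watched.
5. Section 2 rests its double-masking label on two roles, supervisor and assessor. If the first cannot be masked, the label fails on the protocol's own definition.

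**Status of the three roles named**
- Participant: unmasked, as the protocol states.
- Supervisor: unmasked, by the reasoning above.
- Outcomes assessor: can be masked. Nothing in the text contradicts it, though no safeguard is described against participants revealing their arm.

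**The case against.** The strongest case on the other side accepts the inconsistency and disputes its weight.

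- **Outcome assessment is intact.** The primary outcome, the Digit Symbol Substitution Test (DSST), is given by an assessor whose blinding is not contradicted, and section 8 ties masking to objective outcome evaluation. This stands: the error does not invalidate the DSST or Stroop scores.
- **The route to bias is thin.** Intensity is fixed by a heart-rate target and checked by two devices, which leaves mainly encouragement, and nothing in the document gives that a direction or a size. This stands in part. Monitoring limits differences in pacing but not in encouragement or support for adherence, and the lack of a computable size does not make the masking statement true.
- **The label is not bare.** Section 2 says that participants knew their arm and names the masked roles, so a careful reader is not misled about participants. That is right, and the label problem follows from the supervisor claim rather than being a second defect.
- **The supervisor may have been kept unaware of something else, such as the hypothesis.** That is possible, but both sections say that the blinding was to group assignment.
- **Warm-up and cool-down may have differed.** The text does not say whether they were given per session or per day, so it cannot be claimed that they were identical in amount. If they were given per session, the supervisor's mask is weaker still.
- **The session counts do not measure the error.** Agreed. They describe the contrast and assume full attendance.

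**Conclusion.** The concern holds. The protocol states twice that the supervisor was blinded to group assignment, and the design cannot provide this. Double masking should not be claimed; at most, masking of the outcomes assessor can be.

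In size, one of the two masked roles is lost, so two of the three roles named (participant and supervisor) know the arm. Any resulting bias cannot be quantified or given a direction from the document. The consequence is a limit on how much protection against performance bias the as-effective comparison can claim.

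The conclusion assumes that a supervisor is present for at least one complete session and that no undescribed procedure hid its length. It also takes the assessor's blinding as stated; that mask is feasible rather than assured. The correction should be made, but it does not overturn the primary outcome.

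**What to change.** In sections 2 and 8:

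1. Delete the statement that the exercise supervisor was blinded to group assignment. If something other than the assignment was withheld, such as the hypothesis, say what it was and how it was withheld.
2. Replace the double-masking label with wording such as: single-masked (outcomes assessor only); participants and exercise supervisor were not masked.
3. State whether the supervisor was kept out of DSST and Stroop testing, and state it as fact only if it is true.
4. Acknowledge possible performance bias from unmasked participants and supervisor as a limitation on the between-arm conclusion.

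The cost is wording in two sections and a less favourable description of masking. Analysis, sample size and outcomes do not change.
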